#### 7.6.5 Safety assessments specific to this trial

Among glucocorticoid-related side effects, the number of occurrence and proportion of new conditions that require treatment will be individually assessed separately from general safety assessments. Such conditions include; diabetes, hypertension, dyslipidemia, sleep disorders, pathological fractures, and infections. In addition, bone density of the lumbar spine will be measured to evaluate steroidal osteoporosis (at 0, 12, 24 months).

## 8. Management and Report in Case of Adverse Events

## 8.1 Definition of adverse event

An adverse event refers to any unfavorable or unintended sign (including an abnormal laboratory finding), symptom, or disease that occurs after the trial participation, regardless of whether it has a causal relationship with the trial medication. Adverse events occurred by the completion date of the trial medication administration will be observed until 4 weeks after the final administration. When the adverse event persists, the observation should be continued beyond 4 weeks until recovery, wherever possible. Even if an adverse event occurs after the completion of trial medication administration, follow-up observation shall be continued wherever possible in case the causal relationship with the trial medication cannot be denied. However, this is not applied in following cases; symptoms have become chronic due to exacerbation of primary disease or complications, or follow-up observation is difficult due to transferring to another hospital or commencement of a post-trial treatment.

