## 7.2 Clinical assessments and laboratory evaluations during the study period

During the study period, the following clinical assessment and laboratory evaluations are performed as specified for each evaluation time point (at 0, 1, 2, 4, 6, 9, 12, 18, and 24 months, and when a relapse is confirmed; \* 0 month = day  $1\pm 3$  days, 1 month = day  $30\pm 7$  days, 2 months = day  $60\pm 15$  days, 4 months = day  $120\pm 15$  days, 6 months = day  $180\pm 15$  days, 9 months = day  $270\pm 30$  days, 12 months = day  $360\pm 30$  days, 18 months = day  $540\pm 30$  days, 24 months = day  $720\pm 30$  days). During the maintenance treatment period (from month 6 to month 18), interval of hospital visits should not exceed 3 months at a maximum.

- · Confirmation of medication adherence
- · Confirmation of concomitant medications

• Presence or absence of additional treatment for ANCA-associated vasculitis not included in study protocol

- · Observation of adverse events
- Body weight
- Vital signs (blood pressure, pulse, body temperature)
- Blood tests:

<Blood cell count> Red blood cells, hemoglobin, platelets, white blood cells, differential leukocyte counts, number of B cells

<Serum biochemical examinations> Total protein, albumin, electrolytes [Na, K, Cl], BUN, serum creatinine level, CPK, total bilirubin level, AST, ALT, ALP, LDH, γ-GTP, CRP, Ig-G, Ig-A, Ig-M, C3, C4, complement titer, T-Cho, LDL-C, HDL-C, TG, blood glucose, HbA1c, and MPO-ANCA and PR3-ANCA measured by ELISA (or CLEIA, FEIA)

Note that MPO-ANCA and PR3-ANCA data at the time of screening can be used as substitutes for data at 0 months.

• Urinary examinations: General urine tests (glucose, protein, occult blood), urinary sediment, urinary creatinine

- BVAS ver3
- VDI (at 0, 6, 12, 18, and 24 months only)
- SF-36 (at 0, 6, 12, 18, and 24 months only)
- $\cdot$  VAS

• Bone density of the lumbar spine (at 0, 12, and 24 months; images taken during day 1–28 are acceptable as 0-month data.)

- Pregnancy test1)
- Confirmation of survival, ESRD, remission or relapse
- 1) A urine pregnancy test will be performed (hCG  $\geq$ 25 IU/L).

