## 7.3 Clinical assessments and laboratory evaluations at completion or discontinuation of the study

The following tests are performed as specified at the end of the study or when the study is discontinued.

- Confirmation of medication adherence
- Confirmation of concomitant medications
- Presence or absence of additional treatment for ANCA-associated vasculitis not included in study protocol
- · Observation of adverse events
- Body weight
- Vital signs (blood pressure, pulse, body temperature)
- Blood tests:

<Blood cell count> Red blood cells, hemoglobin, platelets, white blood cells, differential leukocyte counts, number of B cells

<Serum biochemical examinations> Total protein, albumin, electrolytes [Na, K, Cl], BUN, serum creatinine level, CPK, total bilirubin level, AST, ALT, ALP, LDH, γ-GTP, CRP, Ig-G, Ig-A, Ig-M, C3, C4, complement titer, T-Cho, LDL-C, HDL-C, TG, blood glucose, HbA1c, and MPO-ANCA and PR3-ANCA measured by ELISA (or CLEIA, FEIA)

• Urinary examinations: General urine tests (glucose, protein, occult blood), urinary sediment, urinary creatinine

- BVAS ver3
- VDI
- SF-36
- $\cdot$  VAS

• Bone density of the lumbar spine (at 0, 12, and 24 months; images taken during day 1–28 are acceptable as 0-month data.)

- Pregnancy test
- · Confirmation of survival, ESRD, remission or relapse

1) A urine pregnancy test will be performed (hCG  $\geq$ 25 IU/L).

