#### 8.3 Emergency report and management of adverse events

## 8.3.1 Scope of adverse events to be reported

Adverse events that the principal investigator or co-investigators are obligated to report to the coordinating investigator or others are the adverse events classified as serious. No mandatory reporting is required for adverse events occurred after completion of the observation period.

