## [Safety]

- ① The number of occurrence and proportion of adverse events and serious adverse events that occurred (at 6 and 24 months)
- 2 Proportions of new-onset diabetes, hypertension, and dyslipidemia requiring treatment (at 6 and 24 months)
- ③ Proportion of sleep disorder requiring treatment (at 6 and 24 months)
- ④ Proportion of pathological fractures and bone density of the lumbar spine (at 24 months)
- (5) The number of occurrence and proportion of infections (intravenous or oral antibiotics are used) (at 6 and 24 months)

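### Sections 8.1 and 8.3.1 set limits on adverse event follow-up and reporting that conflict with the visit schedule and the 24-month safety endpoints

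*Protocol*

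**What the plan says.** **The limiting passages**

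- Section 8.1: "Adverse events occurred by the completion date of the trial medication administration will be observed until 4 weeks after the final administration". It goes on: "When the adverse event persists, the observation should be continued beyond 4 weeks until recovery, wherever possible". For an event that begins after trial medication has been completed, "follow-up observation shall be continued wherever possible in case the causal relationship with the trial medication cannot be denied".
- Section 8.3.1, on which serious events must be reported to the coordinating investigator: "No mandatory reporting is required for adverse events occurred after completion of the observation period".

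**The passages that run to month 24**

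- Section 7.2: the assessments "are performed as specified for each evaluation time point (at 0, 1, 2, 4, 6, 9, 12, 18, and 24 months" and at relapse. The list includes "Observation of adverse events" with no restriction by month, whereas VDI, SF-36 and bone density in the same list are restricted.
- Section 7.3: "The following tests are performed as specified at the end of the study or when the study is discontinued". Adverse event observation is on that list too.
- Section 8.2: events are investigated and entered on the case report form. No time limit or causality condition is attached.
- Section 9.2, under safety: "The number of occurrence and proportion of adverse events and serious adverse events that occurred (at 6 and 24 months". Infections are also counted at 6 and 24 months. Under efficacy, 9.2 lists time to the first serious adverse event from randomisation, and the proportion with serious events, alone and within a composite, at 24 months.

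**The treatment schedule and analysis set**

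- Section 6.3 gives maintenance rituximab at months 6, 12 and 18, and a split second half may follow within two weeks.
- Section 6.4 makes an investigator's finding that rituximab must stop a ground for discontinuing the study.
- Section 10.1.3 keeps everyone who received at least one dose in the safety analysis set.

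**The concern.** The protocol defines an adverse event without regard to causality (7.6.1 and 8.1) and counts such events to month 24. Section 8.1 nevertheless ties observation to the date of the last dose, and for later onsets it brings in a causality judgement. Under 7.6.4 that judgement is a binary call, and in an open-label trial it is made by an investigator who knows the arm. Section 8.3.1 then removes a reporting duty after a period that the reader cannot date.

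A site working from 8.1 and 8.3.1 could reasonably do less after the last dose than a site working from 7.2 and 8.2. Section 10.5.2.3 says that fewer glucocorticoid adverse effects are expected in the low-dose group, so the safety comparison is much of the case for that regimen. If late events are sought unevenly across sites, or according to when a patient stopped rituximab, the 24-month proportions become hard to interpret. The proportions are the more exposed endpoints. For time to first serious event, 9.2 censors at the last day on which absence was confirmed, which gives some protection if sites date it carefully. A 24-month proportion has no such rule.

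**Working it through.** The protocol gives no figure for the length of adverse event capture, so there is none to reproduce. The check is calendar arithmetic, followed by a comparison of the passages.

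**Inputs**

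- Month 18 = day 540 ± 30 and month 24 = day 720 ± 30 (7.2). Month 6 = day 180 ± 15.
- Last scheduled rituximab: month 18, with an optional second half up to 14 days later (6.3).
- Induction: first rituximab on day 1 to 7, then weekly to four doses (section 6 and 6.1).
- Window in 8.1: 4 weeks = 28 days.
- Assumptions: *trial medication* means rituximab, induction doses are exactly a week apart, and the ±30-day visit tolerance is applied to the dose date for the range.

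**Formula:** end of window = day of last dose + 28; interval to the 24-month endpoint = 720 − end of window.

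| Last rituximab | End of 8.1 window | Interval to day 720 | Share of 720 days |
|---|---|---|---|
| Day 540, single dose | 540 + 28 = 568 | 152 days | 21.1% |
| Day 554, split dose | 554 + 28 = 582 | 138 days | 19.2% |
| Day 510, earliest in tolerance | 538 | 182 days | 25.3% |
| Day 584, latest in tolerance plus split | 612 | 108 days | 15.0% |
| Day 180, stops after the month-6 dose | 208 | 512 days | 71.1% |
| Day 22, induction only, first dose day 1 | 50 | 670 days | 93.1% |
| Day 28, induction only, first dose day 7 | 56 | 664 days | 92.2% |

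On the full schedule the 6-month safety endpoint lies well inside the window. For a patient who receives induction only, the window closes 124 to 130 days before day 180 (180 − 56 and 180 − 50), so the 6-month endpoint is affected as well.

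**What governs the interval**

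1. *Full schedule, after day 568 or 582.* Section 7.2 requires adverse event observation at month 24, so the interval is not without a scheduled look. It is the only scheduled look, because the three-month cap on visit spacing in 7.2 covers months 6 to 18. Under 8.1, continued follow-up of an event starting in this interval is asked for where causality cannot be ruled out. Under 8.3.1, whether a serious event must be reported depends on what the observation period is.
2. *What the observation period is.* If it is the 28 days in 8.1, reporting ends at day 568 or 582. Section 6.3, however, describes the maintenance phase as an observation period following treatment, and on that usage reporting would run through maintenance. Section 3 puts maintenance after the trial, which points the other way. No passage settles it.
3. *Early stoppers.* Section 6.4 treats the decision to stop rituximab as discontinuing the study, and 7.3 then provides one assessment. No passage says that the 7.2 visits continue. Section 10.1.3 still keeps these patients in the safety set from which the 24-month proportions are drawn.

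**The case against.** The strongest reply is that 8.1 is a rule about how long to follow events already under way, not a cut-off for recording new ones. Its first sentence concerns events that have occurred by completion of medication, the next extends follow-up until recovery, and the causality clause governs continued follow-up of an event that has already arisen. Recording is dealt with in 8.2, without a causality or time filter, and 7.2 and 7.3 schedule observation to month 24 and at discontinuation. Section 8.3.1 sits under emergency reporting and does not govern the case report form.

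Most of this stands, and it rules out three stronger readings that a reader might infer:

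- *That adverse events are observed for four weeks and no longer, so late events are lost.* The text of 8.1 does not say so, and 7.2 and 8.2 point the other way.
- *That about a fifth of follow-up has no mandatory capture, from which a loss of serious events could be calculated.* The month-24 visit falls in that interval. Such a calculation would also need zero capture after the window and a serious event risk that the protocol does not give.
- *That the window differs by arm because low-dose prednisolone ends earlier.* This needs *trial medication* to include prednisolone. Section 5.1 identifies rituximab as the investigational product, 7.6.4 names glucocorticoids separately from trial medication, and the rituximab schedule is the same in both arms.

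The reply does not remove the conflict. The follow-up reading of 8.1 is possible but not stated. The observation period remains undated, and no passage provides adverse event collection after the single discontinuation assessment.

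**Conclusion.** This is an internal contradiction that should be resolved, not demonstrated under-counting. Sections 8.1 and 8.3.1 can be followed in a way that leaves late events without further follow-up or reporting, while 7.2, 8.2 and 9.2 presuppose collection to month 24. On the full rituximab schedule the passages conflict over about the last 138 to 152 days (108 to 182 days if the visit tolerance applies to dosing). For a patient with induction doses only it is 664 to 670 days. These figures give the length of the interval in dispute, not the share of events missed. They rest on *trial medication* meaning rituximab and, for induction, on exact weekly dosing.

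Capture in that interval may be inconsistent across sites, above all in patients who stop rituximab early. The 6-month primary endpoint does not depend on these passages, and 6-month safety is inside the window for patients on the full schedule.

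**What to change.** Reconcile 8.1 and 8.3.1 with 7.2, 7.3, 8.2 and 9.2:

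1. Define *trial medication* and *observation period* once, and use them consistently.
2. State in 8.1 and 8.3.1 that all adverse events and serious adverse events are recorded, and serious ones reported, through the 24-month visit in both arms, regardless of treatment status or judged causality, unless consent is withdrawn.
3. Keep the existing follow-up-until-recovery text as a separate rule on how long an individual event is pursued, so that it is not read as a limit on recording.
4. Make clear, with reference to 6.4 and 7.3, that stopping rituximab does not by itself end adverse event collection.

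The cost is wording, a small extra reporting load after month 18, and continued contact with patients who stop early. For patients who stay on schedule, the month-18 and month-24 visits already exist. No dose, schedule or treatment rule changes.

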## 8.2 Assessment and report of adverse events

When an adverse event occurred, the principal investigator and co-investigators investigate the event and describe it on a case report form, which should include the following details. If the study medication is discontinued or the adverse event requires a treatment, the subject shall be informed of it.

- (1) Name of adverse event
- (2) Date of occurrence

- (3) Outcome (recovering/resolving, recovered/resolved, not recovered/not resolved, fatal)
- (4) Action taken regarding the trial medication: Dose increased, dose reduced, dose not changed, medication interrupted, medication discontinued
- (5) Concomitant treatment: Details of any concomitant treatments that was being performed at the time or immediately before the event occurred
- (6) Severity: Severity shall be judged based on CTCAE v4.0 Japanese Translation JCOG version.
- (7) Seriousness classification: Serious adverse events are defined as adverse events that cause death; life-threatening condition; disabilities; a condition potentially leading to disabilities; requires hospitalization or prolongation of existing hospitalization, any other serious conditions according the forgoing examples, and causes congenital diseases or anomalies in a later generation.

#### 8.3 Emergency report and management of adverse events

## 8.3.1 Scope of adverse events to be reported

Adverse events that the principal investigator or co-investigators are obligated to report to the coordinating investigator or others are the adverse events classified as serious. No mandatory reporting is required for adverse events occurred after completion of the observation period.

## 8.3.2 Actions to be taken in case of occurrence of serious adverse events

- (1) When a serious adverse event occurred, the principal investigator or co-investigators perform appropriate procedures, regardless of causal relationship with the study medication, and engage in investigation of the causes.
- (2) The principal investigators of each site are required to report the adverse event information to the Coordinating Office, the head and IRB of each site. Reports to be submitted are the first report (an emergency report and an adverse event report form which is filled in as much as possible, are submitted via either e-mail, telephone, or FAX) and the second report (a detailed report, the adverse event report form which is fully completed, and an adverse event detailed report form, are submitted via either e-mail, telephone, FAX, or in person). For a lethal adverse event, the principal investigator or co-investigators should submit the first report within 72 hours after the event was identified. The second report should be submitted within 15 days.
- (3) The trial coordinating office and the coordinating investigator report the event information as promptly as possible to the principal investigators of study sites other than the one where the adverse event occurred. Depending the urgency, reporting over telephone is acceptable; however,

a written report should follow as soon as possible (via either e-mail, FAX, mail, or in person). The principal investigators of each site report the event to the head of own institution.

The coordinating investigator/committee determine the extent of urgency, significance, impact, etc. of the reported event, and take measures such as temporary suspension of patient enrollment and emergency contact to the participating site to inform necessary information.

## 8.4 Review by Efficacy and Safety Assessment Committee

If judgement of the appropriateness of continuing enrollment or the necessity of any protocol revision is required, the Efficacy and Safety Assessment Committee reviews the report contents, and makes recommendations in writing to the coordinating investigator, coordinating committee, and the case registration center.

#### 8.5 Anticipated adverse effects

In the package insert of RITUXANa, the following major side effects are described: infusion reaction, exacerbation of hepatitis caused by hepatitis B virus (frequency unknown), liver dysfunction (<5%), mucocutaneous ocular syndrome (frequency unknown), leukopenia ( $\geq 10\%$ ), thrombocytopenia (<5%), infection (frequency unknown), progressive multifocal leukoencephalopathy (frequency unknown), interstitial pneumonia (frequency unknown), cardiac disorder (frequency unknown), renal disorder (frequency unknown), gastrointestinal perforation (frequency unknown), and reversible posterior leukoencephalopathy syndrome (frequency unknown).

Major side effects described in the package insert of Predonine are: infection, secondary adrenal cortex dysfunction, diabetes, gastrointestinal ulceration, gastrointestinal perforation, gastrointestinal bleeding, pancreatitis, dysthymia, depression, convulsion, osteoporosis, aseptic osteonecrosis, myopathy, glaucoma, cataract, central serous chorioretinopathy, thrombosis, myocardial infarction, cerebral infarction, aneurysm, epidural lipoma, and tendon rupture (none of these are subject to frequency survey).

For other anticipated adverse effects, please refer package inserts of rituximab and prednisolone. As a reference, side effects identified in the RAVE trial (Remission induction treatment with the combined use of rituximab + high-dose glucocorticoids in ANCA-associated vasculitis) conducted in the United States are listed below.

< Aggregate calculation of 99 patients with ANCA-associated vasculitis in RAVE trial>

Side effect	Frequency
-------------	-----------

Infection	7/99 patients (7 %)
Leukopenia (Grade ≥3)	3/99 patients (3 %)
Thrombocytopenia (Grade ≥3)	3/99 patients (3 %)
Venous thrombosis	6/99 patients (6 %)
Infusion reaction	1/99 patients (1%)

## 9. Endpoints

## 9.1 Primary endpoint

## [Efficacy]

Number of patients who achieved remission (at 6 months) Remission induction rate (at 6 months)

## Total number of patients

## [Rationale]

This is the most widely used efficacy index in evaluation studies of remission induction treatments for vasculitis, and has been used as a primary endpoint in the majority of similar clinical trials.

## 9.2 Secondary endpoints

## [Efficacy]

- 1 Time to remission
- ② Overall survival period, relapse-free period, time to ESRD, time to the first serious adverse event These endpoints are defined as a length of time from the time of randomization to the occurrence of respective events, and patients who did not experience the event will be counted as censored. Definitions of event and date censored for each endpoint are shown in a table below.

Endpoint	Event (whichever is	Date censored	Competing risk
	earlier if more than one)		
Time to remission	Remission	The last day of confirmed	Death
		absence of remission	
Overall survival period	Any death	The last day of confirmed	None
		survival	
Relapse-free survival	Any death, relapse	The last day of confirmed	None
period		absence of relapse	
Time to ESRD	ESRD	The last day of confirmed	Death

		absence of ESRD	
Time to the first serious	First serious adverse event	The last day of confirmed	None
adverse event	(including death and	absence of serious adverse	
	hospitalization)	event	

- ③ The proportion of death, relapse, ESRD, or serious adverse events, and proportion of a composite outcome thereof (at 6 and 24 months; \*at 6 months, proportions of death, ESRD, and serious adverse events only)
- ④ Proportions of minor and major relapses (at 24 months)
- (5) The proportion of participants who achieved remission and glucocorticoid cessation
- (6) Assessment of disease activity using BVAS ver3 (at 6 and 24 months)
- ⑦ Irreversible damage measured using VDI (at 24 months)
- 8 Evaluation of health-related QOL using SF-36 (at 6 and 24 months)
- 9 Patient general assessment with a VAS (at 6 and 24 months)
- (1) Cumulative glucocorticoid dose (at 6 and 24 months)

## [Safety]

- ① The number of occurrence and proportion of adverse events and serious adverse events that occurred (at 6 and 24 months)
- 2 Proportions of new-onset diabetes, hypertension, and dyslipidemia requiring treatment (at 6 and 24 months)
- ③ Proportion of sleep disorder requiring treatment (at 6 and 24 months)
- ④ Proportion of pathological fractures and bone density of the lumbar spine (at 24 months)
- (5) The number of occurrence and proportion of infections (intravenous or oral antibiotics are used) (at 6 and 24 months)

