## 3. Study Design

This is an open-label, randomized trial comparing two arms that undergo remission induction treatment with rituximab + low-dose glucocorticoids or rituximab + high-dose glucocorticoids. After the trial, patients in remission proceed promptly to maintenance treatment.

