## [Rationale]

Among the efficacy-related items, (1) is to supplement the primary endpoint, (2) - (4) are typical non-remission efficacy endpoints. The composite outcome was included to assess the efficacy-safety balance. (5), (6), (7), (8) are indices of the disease activity, irreversible damage caused by the disease, patient QOL [18], and overall patient evaluation, respectively. (9) is considered necessary to prove the hypothesis of this study.

Among the safety-related items, we think that (1) is required for general safety evaluation of a clinical study. (2) - (5) are items to reflect adverse effects of glucocorticoids, which represent a major focus of this

study.			

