#### 10.5.2.3 Secondary safety endpoint analyses

This study is a non-inferiority trial, in which adverse effects of glucocorticoids are expected to be reduced in the low-dose group. The adjustment of multiplicity will not be performed in the analyses on the secondary safety endpoints. The significance level in the hypothesis test will be 5% (two-sided), and confidence intervals to be calculated are two-tailed 95% confidence intervals.

The number of cases in which adverse events and serious adverse events occurred and proportions of those with and without occurrence, etc. are aggregated in a group-by-group manner, and Pearson's chi-square test will be used for intergroup comparisons (or Fisher's exact test, when cells with an expected frequency less than 5 account for 20% or more).

For occurrence of new-onset diabetes requiring treatment, hypertension, dyslipidemia, sleep disorder

requiring treatment, pathological fractures, and infections (intravenous or oral antibiotics are used), the number of cases and proportions of cases with and without occurrence in each group are determined, and Pearson's chi-square test will be used for intergroup comparisons (or Fisher's exact test, when cells with an expected frequency less than 5 account for 20% or more).

For bone density of the lumbar spine, the data will be aggregated using summary statistics for each group, and compared between the groups by the analysis of variance model.

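### Open-label trial: four steroid-toxicity endpoints count only conditions needing treatment, with no measured criterion or masked assessment, so arm-dependent prescribing could create or enlarge a safety difference

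*Protocol*

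**What the plan says.** Protocol section 3 describes the design: "This is an open-label, randomized trial comparing two arms that undergo remission induction treatment". Sites and patients therefore know the glucocorticoid arm.

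The safety list in section 9.2 counts "Proportions of new-onset diabetes, hypertension, and dyslipidemia requiring treatment (at 6 and 24 months") and "Proportion of sleep disorder requiring treatment (at 6 and 24 months"). Section 7.6.5, the operational section, adds only that "the number of occurrence and proportion of new conditions that require treatment will be individually assessed separately from general safety assessments". The synopsis and sections 2.2 and 10.5.2.3 carry the same definition. None of these places gives a laboratory or blood pressure value, a diagnostic criterion, a rule for starting treatment, or an assessor masked to arm.

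The rationale in section 9.2 gives these endpoints weight. Of the safety items it says "2) - (5) are items to reflect adverse effects of glucocorticoids, which represent a major focus of this" study. Section 10.5.2.3 states that "adverse effects of glucocorticoids are expected to be reduced in the low-dose group". It tests the items by Pearson chi-square (Fisher's exact test when expected counts are small) at two-sided 5%, without multiplicity adjustment.

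Section 7.2 and the schedule in section 23.1 require blood pressure and "T-Cho, LDL-C, HDL-C, TG, blood glucose, HbA1c" at months 0, 1, 2, 4, 6, 9, 12, 18 and 24.

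**The concern.** An event is counted when a new condition is judged to need treatment. With no printed criterion, two patients with the same glucose, lipid or blood pressure value can be classified differently, and whoever judges them knows the arm. The scheduled regimens give a plausible reason for unequal judgement. In weeks 21-24 the table in the glucocorticoid dosing section has one arm at 0 mg and the other at 10 mg/day, so the exposure still to come differs at the same measured value.

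The definition is fixed in five places and its test is fixed too, so this is a stated choice and not a detail left to the statistical analysis plan. Followed exactly, it yields a comparison that mixes steroid toxicity with prescribing habit.

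At stake is how the safety result is read. Section 1.3 justifies the trial by the need to reduce toxicity, and section 10.5.2.1 tolerates a remission rate up to 20 points lower. A credible reduction in steroid toxicity is therefore a large part of the argument for the low-dose regimen. Data that could corroborate it are already collected.

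**Working it through.** **1. The plan's own figure.** The protocol gives no planned rate or power for these safety endpoints. The sample size is needed only to fix n. With 0.80 in both arms, margin 0.2, one-sided 0.025 and power 0.80:

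n = 2 × 0.8 × 0.2 × (1.960 + 0.842)² / 0.2² = 62.8, so 63 per arm; 63 / 0.9 = 70 per arm, 140 in total.

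This reproduces sections 3.1 and 10.2 and is not in dispute.

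**2. Test.** Let A and B be the event counts in the high- and low-dose arms and s = A + B. With n per arm, the Pearson statistic is X² = 2n(A − B)² / [s(2n − s)], and the test rejects when X² > 3.841. The rejection probability is the exact sum of Bin(A; n, p_H) × Bin(B; n, p_L) over rejecting pairs. At 15% the expected count per arm is 70 × 0.15 = 10.5, so the switch to Fisher's test would seldom apply and is ignored.

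**3. Illustration A: a direct shift in counted events.** The true rate is 15% in both arms, n = 70. The rates are assumed; the documents give none.

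| Counted, high dose | Counted, low dose | P(significant) | of which favouring low dose |
|---|---|---|---|
| 15% | 15% | 0.049 | 0.025 |
| 20% | 15% | 0.121 | 0.118 |
| 25% | 15% | 0.319 | 0.318 |
| 30% | 15% | 0.577 | 0.577 |

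**4. Illustration B: equal true incidence, unequal chance of treatment.** The counted rate is incidence × probability of treatment. With 30% incidence in both arms (assumed) and n = 70:

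| Treated, high v low | Counted rates | P(significant) |
|---|---|---|
| 70% v 70% | 21% v 21% | 0.051 |
| 80% v 60% | 24% v 18% | 0.142 |
| 80% v 50% | 24% v 15% | 0.271 |
| 90% v 50% | 27% v 15% | 0.421 |

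Over assumed incidences of 20-50%, a 20-point treatment gap gives about 10-24% and a 30-point gap about 18-48%.

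**5. Would a purely measured endpoint be unbiased?** No. Suppose 20% would cross a threshold in both arms, but earlier treatment in the high-dose arm holds its crossings to 15% or 10% (assumed). The same test then rejects in 12% (0.121) or 38% (0.382) of trials, nearly always against low dose. The bias has changed sign.

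**6. Where the measurements go.** Section 10.5 names between-arm analyses for BVAS, VDI, SF-36, VAS, cumulative glucocorticoid dose, lumbar bone density, eGFR, IgG and B cell count. HbA1c, glucose, lipids and blood pressure are not among them. They reach the analysis indirectly in two ways. Abnormal laboratory findings can be adverse events graded by CTCAE (section 7.6.1). The VDI form (section 23.3) has a diabetes item and a hypertension item met by diastolic pressure of 95 mmHg or by antihypertensive use. For bone, the protocol does pair a clinical event (fracture) with a measurement (bone density).

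**The case against.** **The measurements are not unused.** A reader might infer from their absence in section 10.5 that they serve no analysis. That goes too far, given the adverse-event and VDI routes. Both routes are recorded at the site with the arm known, however, and the VDI hypertension item can be met by medication alone. They therefore do not supply the missing check.

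**The statistical analysis plan may add laboratory summaries.** Section 10.5 lists major methods only, so silence on a laboratory table is no error. This stands. The point rests on the printed event definition, which extra summaries would leave unchanged.

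**The text does not say that a prescription is the event.** It asks for a new condition and a need for treatment. That the treating physician decides is a fair inference, since no central or masked assessor is named for these endpoints, but it is not a written rule.

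**Direction and size are not shown.** Section 10.5.2.3 states an expectation about adverse effects, not about prescribing. The rates in the illustrations are assumed, and the 58% case needs knowledge of the arm alone to double the event rate. This stands in full.

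**Safety does not rest on these four items.** Serious adverse events, deaths, infections, fractures and measured bone density also contribute. That limits the consequence, but the protocol still counts these items within a major focus.

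**Conclusion.** The concern holds in a limited form. Because treatment need is the only criterion and nobody is masked, arm-dependent prescribing could create or enlarge a difference in these four endpoints, plausibly in favour of low dose. The calculations show only what an assumed gap would do: no gap leaves the test at about 5%, and a gap of 5 to 15 points in counted events raises rejection to about 12-58% at 70 per arm. The true gap is not in the documents.

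Three stronger readings are not supported. One is that the bias is established and certainly favours low dose; that is plausible, not shown. Another is that conclusions should rest on a measured version alone; step 5 shows that this can be biased the other way. The third is that the primary conclusion is compromised; it does not use these endpoints. For sleep disorder only the first half of the point applies, because no measurement is scheduled for it. This is an inexpensive improvement to how the safety result is supported, not an error in the primary analysis.

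**What to change.** In sections 9.2 and 10.5.2.3, keep the treatment-based endpoints and add these pre-specified supportive analyses of data already collected:

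- **Measured values:** a between-arm comparison over time of HbA1c or glucose, LDL-C and blood pressure.
- **Programmed events:** for patients below threshold at month 0, an event defined as either a threshold crossing at a scheduled visit or any treatment start, shown beside a version that counts crossings only. The sponsor sets the thresholds before data fixation, and a program applies them identically in both arms.
- **Claim rule:** state a reduction in diabetes, hypertension or dyslipidaemia only where the treatment-based and measured results agree.
- **Sleep disorder:** label the result as open to prescribing bias.

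The cost is wording, some programming and a few extra tables. No visit or test is added and patient care is unchanged. Treatment started below a threshold can itself lower later values, so the versions bracket the bias and do not remove it. Two limits should be stated with the results: section 7.2 specifies no fasting for glucose or lipids, and the month-0 values may follow up to 7 days of permitted pre-enrolment prednisolone.
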